# 11 HEALTH OUTCOMES

### 11.1 QUALITY OF LIFE MEASURES

Quality of life was assessed using SGRQ. The analyses of SGRQ are described in Section 10.3.2.

### **11.2 RESOURCE UTILIZATION MEASURES**

Hospitalizations and hospitalizations related to cardiopulmonary indications are collected during the study. The analysis is discussed in Section 12.6.2.

#### 12 SAFETY ANALYSES

All safety analyses will be performed only on the Safety population (see Section 6).

### **12.1 EXTENT OF EXPOSURE**

All study drug dosing will be listed for all subjects. The listing will include initial dose (number of breaths for each session and number of breaths for the day) and date of this initial dose and dose and date of each subsequent dose change. Dosing at Weeks 4, 8, 12, 15, and 16 will be summarized for subjects still receiving study drug at each of these assessments. The summary will include both the numeric summaries and the categorical summaries for number of breaths per session as well as the number of breaths per day. If study drug is dosed differently across different sessions on the same day, the maximum number of breaths is used for summarization. Summary of overall duration of exposure will be included as well as the

final dose (breath/session) and the maximum study drug dose (breath/session) reached for each subject (numerically and categorically).

For study treatment compliance, the number and percentage of days with dose >0 breaths will be calculated and summarized.

#### **12.2 ADVERSE EVENTS**

All AEs will be coded to the appropriate PT and SOC using MedDRA. AEs will be listed by treatment group including all details recorded on the eCRF plus an indicator of whether the event was treatment-emergent. The AE listings will include the AE verbatim term and its corresponding PT and SOC.

The AE summaries will be limited to include only treatment-emergent AEs. Treatmentemergent AEs are those AEs with onset date equal to or after the start date of the study drug. The non-treatment-emergent AEs (the AEs occur after signing the informed consent form but before receiving study drug) will be listed but not included in summary tables.

All summaries will include the number and percentage of subjects experiencing each type of adverse event and the total number of each type of adverse event, in order of overall frequency and/or SOC. Serious adverse events (SAE) and non-serious AEs will also be summarized by SOC and PT.

The total number of AEs and the AE rates will be calculated and summarized for each display, as appropriate. The AE rate will be calculated as the total number of AEs divided by the total patient years of exposure to study drug per treatment group.

Adverse events possibly or probably related to study drug will be summarized. An AE summary by severity (mild, moderate, and severe) will also be provided.

Separate listings and summary tables will be provided for all SAEs, AEs leading to the discontinuation of study drug, and all deaths during the study (if data permit). For listing of deaths, information for all subjects who die during the study period from the randomization to the end of study (including 30 days after the last study treatment dosing) will be included.

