9.2 DOCUMENTATION OF ADVERSE EVENTS

An AE or SAE occurring during the study must be documented in the subject's source documents and on the appropriate eCRF page. Information relating to the AE such as onset and cessation date and times, intensity, seriousness, relationship to study drug, and outcome is also to be documented in the eCRF (see Appendix 15.2 for definitions). Where possible, AEs should be recorded using standard medical terminology. The Investigator should attempt, if possible, to establish a diagnosis based on the presenting signs and symptoms. If several signs or symptoms are clearly related to a medically-defined diagnosis or syndrome, the diagnosis or syndrome should be recorded on the eCRF page, not the individual signs and symptoms.

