15.2 GUIDELINES AND DEFINITIONS FOR RECORDING ADVERSE EVENTS

The Investigator or a designated member of his/her staff will probe each subject for any AEs that may have occurred. The Investigator should always ask the same question when conducting the verbal probe in order to ensure uniformity between subjects. The Investigator should ask:

"How are you doing (feeling)?"

Based on the subject's response to this question, the Investigator should ask additional questions relevant to the specific complaint such as:

"How severe is/was the symptom?"

"How often did the symptom occur?"

"How long did the symptom last?"

It is the Investigator's responsibility to review the results of all diagnostic and laboratory tests as they become available and ascertain if there is a clinically significant change from Baseline. If the results are determined to be a clinically significant change from Baseline, this should be reported as an AE. The Investigator may repeat the diagnostic procedure or laboratory test or request additional tests to verify the results of the original tests. When possible, a diagnosis associated with the abnormality should be used as the reported AE.

Using provided definitions, the Investigator will then:

(1) rate the intensity and seriousness of the AE, (2) estimate the causality of the AE to study drug, and (3) note actions taken to counteract the AE.

Definitions of Intensity, Seriousness, Causality, Action Taken, and Outcome

INTENSITY

An assessment of the relative intensity (severity) of an AE is based on the Investigator's clinical judgment. The maximum intensity encountered during the evaluation period should be checked. The assessment of intensity should be independent of the assessment of the seriousness of the AE.

SERIOUSNESS

A serious AE is one that represents an actual or potential significant hazard. This includes, but is not limited to, an event that is fatal, life-threatening, permanently or severely disabling, requires or prolongs inpatient hospitalization*, is a congenital abnormality (offspring of subject) or is medically significant (important medical events that may not result in death, be life-threatening, or require hospitalization may be considered an SAE when, based upon appropriate medical judgment, they may jeopardize the subject and may require medical or surgical intervention to prevent 1 of the outcomes listed in this definition).

*Hospitalizations that would not be considered SAEs include those for:

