14.2.1.17	Summary of Effects of Baseline Hemodynamics and Baseline PFTs on Peak 6MWD by Week
14.2.2.1	Summary and Analysis of Peak 6MWD (meter) at Week 12 – Secondary Efficacy Endpoint
14.2.2.2	Summary and Analysis of Peak 6MWD (meter) at Weeks 4 and 8
14.2.3.1	Summary and Analysis of NT-proBNP (pg/mL) Data at Week 16 – Secondary Efficacy Endpoint
14.2.3.2	Summary and Analysis of NT-proBNP (pg/mL) Data at Week 16 – with Observed Case
14.2.3.3	Summary and Analysis of NT-proBNP (pg/mL) Data at Week 8
14.2.3.4	Summary and Analysis of NT-proBNP (pg/mL) Data at Week 8 with Observed Case
14.2.4.1	Summary and Analysis of Trough 6MWD (meter) at Week 15 – Secondary Efficacy Endpoint
14.2.4.2	Summary and Analysis of Trough 6MWD (meter) at Week 15 with Observed Case
14.2.5.1	Summary and Analysis of Clinical Worsening Events
14.2.5.2	Summary of Hospitalization Information
14.2.6.1	Summary and Analysis of SGRQ Total Score
14.2.6.2	Summary and Analysis of SGRQ Symptoms Score
14.2.6.3	Summary and Analysis of SGRQ Activity Score
14.2.6.4	Summary and Analysis of SGRQ Impacts Score
14.2.7	Summary and Analysis of Distance Saturation Product (DSP) (m%)
14.3.1.1	Overall Summary of Adverse Events and Exacerbations of Underlying Lung Diseases
14.3.1.2	Summary of Adverse Events by System Organ Class and Preferred Term
14.3.1.3	Summary of Adverse Events by Preferred Term
14.3.1.4	Summary of Deaths
14.3.1.5	Summary of Serious Adverse Events by System Organ Class and Preferred Term
14.3.1.6	Summary of Non-Serious Adverse Events by System Organ Class and Preferred Term
14.3.1.7	Summary of Adverse Events Probably or Possibly Related to Study Drug by System Organ Class and Preferred Term

Table Number	Table Title
14.3.1.8	Summary of Adverse Events Leading to Permanent Discontinuation of Study Drug by Preferred Term
14.3.1.9	Summary of Adverse Events by System Organ Class, Preferred Term, and Severity
14.3.1.10	Summary of Adverse Events by Study Drug Dose at AE Onset
14.3.2.1	List of Deaths
14.3.2.2	List of Serious Adverse Events
14.3.4.1	Summary of SpO2 (%) Measured by Pulse Oximetry
14.3.4.2	Categorical Summary of SpO2 (%) Measured by Pulse Oximetry
14.3.4.3	Summary of Heart Rate (beats/min) by Pulse Oximetry
14.3.4.4	Summary of Supplemental Oxygen Use
14.3.4.5	Summary of Supplemental Oxygen (L/min)
14.3.4.6	Summary of Pulmonary Function Test Results
14.3.4.7	Summary of Subjects with ≥20% Decrease in FEV1 from Baseline
14.3.4.8.1	Summary of Laboratory Data – Clinical Chemistry

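### SAP 12.2 defines treatment-emergent AEs by onset date alone, so on-drug worsening of an AE already recorded in screening can be missing from the AE summaries if that AE is kept as one record.

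*SAP*

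**What the plan says.** SAP 12.2 limits the AE summaries to treatment-emergent events, defined as "those AEs with onset date equal to or after the start date of the study drug". AEs with onset between consent and study drug "will be listed but not included in summary tables". The same section gives a rate: "The AE rate will be calculated as the total number of AEs divided by the total patient years of exposure" to study drug in each treatment group. It also plans summaries by severity and by relationship to study drug. The protocol does not define treatment-emergent AEs.

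Under Protocol 3.3.2.7, AEs are recorded from signature of the consent form. The notes to the schedule in Protocol 3.2 allow Screening up to 30 days before the first dose, or 48 hours when Screening and Baseline are combined.

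For recording, Protocol 9.2 names "Information relating to the AE such as onset and cessation date and times, intensity, seriousness, relationship to study drug, and outcome". On intensity, Protocol Appendix 15.2 says: "The maximum intensity encountered during the evaluation period should be checked". Protocol 9.3 has the eCRF pages updated as new information arrives. Protocol 9.1.1 allows worsening of an existing symptom or condition to be an AE.

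**The concern.** A treatment-emergent definition usually has two limbs: new onset after the first dose, and worsening after the first dose of something already present. The SAP has only the first. An AE that starts mildly in screening and becomes severe on drug keeps its screening onset date unless someone opens a new record. It then fails the SAP's test and drops out of the tables that readers use to judge tolerability.

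The development of AEs after treatment is among the primary safety assessments in Protocol 3.3.2. Any loss of this kind runs one way: it understates worsening on drug.

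**Working it through.** The plan states no figure for this point, so the check sets the texts side by side. The arithmetic at the end only shows scale.

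**1. Apply the rule to one case.** Suppose a headache is recorded as mild in screening, is still ongoing at the first dose, and becomes severe on drug.

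| How the site enters it | Onset date | SAP 12.2 test | Where it appears |
|---|---|---|---|
| One record, updated | Before first dose | Not treatment-emergent | Listing only |
| New record for the worsening | After first dose | Treatment-emergent | Listing and all AE summaries |

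**2. Which entry do the documents require?**
- Protocol 9.1.1 makes worsening a possible AE. It says nothing about a new record or onset date for an AE already recorded.
- Protocol 9.2 names onset, cessation and intensity, but no date of a change in intensity.
- Protocol 3.3.2.7 follows each AE to resolution or until it is no longer clinically significant, Protocol 9.3 updates its pages, and Appendix 15.2 takes its maximum intensity. All three are compatible with one updated record.
- Neither document states either practice as a rule. Two sites could follow the protocol and enter the same event differently.

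**3. Effect on relatedness.** Under its not-related category, Appendix 15.2 lists events that precede the first administration of study drug. A single record with a screening onset therefore points the investigator to that category, even if the drug plausibly caused the worsening. Changing the SAP definition alone would not correct this.

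**4. What is captured anyway.**
- Worsening of a medical-history condition that was never an AE record is a new AE with its own onset date.
- Appendix 15.2 says of diagnostic and laboratory results judged to be a "clinically significant change from Baseline, this should be reported as an AE". Protocol 3.3.2.1 has a similar rule for the Week 16 or early termination physical examination.
- Oxygenation, pulmonary function, laboratory tests, ECG, hospitalizations, vital signs and exacerbations have their own summaries (SAP 12.3 to 12.6), which do not depend on AE onset.

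What remains is mainly a symptomatic AE that was recorded in screening, was ongoing at the first dose, worsened on drug and was not entered again.

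**5. Scale per omitted event.** Inputs: 314 subjects allocated 1:1 and about 15% discontinuation (SAP 5); Week 16 at Day 113 with a window of ±5 days (Protocol 3.2).
- Subjects per arm: 314 / 2 = 157. One omitted subject with no other record of that term: 1 / 157 = 0.64 percentage points.
- Exposure per arm if all complete 112 days: 157 × 112 / 365.25 = 48.1 patient-years. One event: 1 / 48.1 = 2.1 per 100 patient-years.
- If every subject ran to the end of the window, 118 days: 157 × 118 / 365.25 = 50.7 patient-years. One event: 1 / 50.7 = 2.0 per 100 patient-years.
- If 15% stopped at the start and the rest completed 112 days: 48.1 × 0.85 = 40.9 patient-years. One event: 1 / 40.9 = 2.4 per 100 patient-years.

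These are effects per event. They say nothing about how many events are lost.

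**The case against.** The strongest reply is that the protocol already makes worsening an AE. Protocol 9.1.1 does so in three ways. It includes worsening of an existing condition, with greater frequency or intensity as an example. It excludes fluctuations of conditions present at the start only when they do not worsen. It excludes signs and symptoms of the studied disease unless they are more severe than expected. If worsening is an AE, Protocol 9.2 asks for its onset date, and that date falls after the first dose.

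The evidence for one record is also indirect. The evaluation period for maximum intensity is not defined, the instruction to update pages does not forbid new ones, and the list in Protocol 9.2 is not exhaustive. The eCRF is a separate document supplied to sites (Protocol 12.4), and any entry instructions with it are not available here.

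Most of this stands. It narrows the gap to AEs already on record before dosing and makes the loss conditional on how sites enter them. It does not close the gap, because nothing in either document tells a site to give such an AE a new onset date.

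A reader might infer two further faults, neither of which adds to the point:
- That the SAP leaves open whether the serious-AE and discontinuation tables follow the treatment-emergent limit, since it says "Separate listings and summary tables will be provided for all SAEs". But the limit is stated generally for AE summaries, and a serious AE is by definition an AE, so the limit applies to those tables too.
- That the date rule mishandles an AE arising on Day 1 before the dose. That is over-inclusion, opposite in direction to the loss described here, and minor.

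**Conclusion.** The point holds as an optional improvement. As written, the onset-only rule can leave out on-drug worsening of an AE first recorded in screening, provided the site keeps it as one record. The documents fit that practice but do not prove it.

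A reader might infer that on-drug worsening in general is missing from the safety tables. The documents do not support that: Protocol 9.1.1, the change-from-Baseline reporting rules and the separate safety summaries capture much of it.

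The number affected cannot be estimated from the documents and is probably small. Per event, the effect is 0.64 percentage points for a term or 2.0 to 2.4 per 100 patient-years, under the exposure assumptions shown. Protocol 10.3.4 plans no inferential analysis of AEs, and the event stays in the listings with its treatment-emergent indicator.

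**What to change.** In SAP 12.2, define a treatment-emergent AE as one with onset on or after the first dose, or one with earlier onset that worsens in intensity or becomes serious after the first dose.

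In Appendix 15.2 or the eCRF instructions, tell sites to enter such worsening as a new record with the date of worsening as its onset. Count only that post-dose record, so that each worsening enters event totals and rates once. The new record can be assessed for causality afresh. It also supplies a dose for Table 14.3.1.10, "Summary of Adverse Events by Study Drug Dose at AE Onset", which a record with pre-dose onset lacks.

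The cost is one or two SAP sentences, one site instruction and minor programming. For AEs already held as one record, sites must be queried for the date of worsening. Records with onset before and cessation after the first dose, or still ongoing, can be found in blinded data, and their number gives an upper bound on the single-record cases. AE counts may rise slightly.

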3.3.2.7 Adverse Events

Adverse events will be recorded throughout the course of the study from the time that each subject signs the ICF until the time screen failure is documented, or until the subject is either discontinued from the study or all Week 16 study assessments have been completed. Each subject will be questioned for AEs at each scheduled study visit and during required telephone/email contacts. Subjects will also be instructed to spontaneously report all AEs throughout the study.

All AEs should be followed until either resolution (or return to normal or baseline values), until they are judged by the Investigator to no longer be clinically significant, or for at least 30 days if the AE extends beyond the final study visit. All AEs meeting the criteria for serious (ie, serious adverse events [SAEs]) should be followed until resolution, death, or the

subject is lost to follow-up even if they are ongoing more than 30 days after completion of the final study visit (Week 16 or ET). All AEs/SAEs that occur while the subject is in study will be recorded as instructed in this protocol.

Sections 9 and 15.2 provide the guidelines and definitions for recording AEs.

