8 STUDY TERMINATION

8.1 CRITERIA FOR SUBJECT WITHDRAWAL

A subject may voluntarily withdraw or be withdrawn from the study and/or study drug by the Investigator at any time for reasons including, but not limited to, the following:

- The subject wishes to withdraw from further participation.
- A serious or life-threatening AE occurs or the Investigator considers that it is necessary to discontinue study drug to protect the safety of the subject.
- The subject consistently deviated from the protocol.
- Lung transplantation.
- The subject becomes pregnant.
- The subject's behavior is likely to undermine the validity of his/her results.

If a subject is discontinued from the study prematurely, the Investigator must provide an explanation in the eCRF and complete the End of Study Record for that subject. If study drug has been administered, the Investigator should make every effort to perform all scheduled evaluations prior to discharge. In the event that a subject discontinues study drug prematurely due to an AE, the subject will be followed until either the Investigator determines that the AE has resolved, it is no longer considered clinically significant, the subject is lost to further follow-up, or for 30 days if the AE extends beyond the final visit.

If a subject discontinues study drug prematurely for any reason, the subject should be encouraged to remain in the study and attend the remaining scheduled study visits (excluding the Week 15 Visit) up to and including Week 16.

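### The AE rate counts events that start after study drug is stopped but divides by time on study drug only, so its two parts cover different periods

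*SAP*

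**What the plan says.** **Denominator.** SAP 12.2: "The AE rate will be calculated as the total number of AEs divided by the total patient years of exposure to study drug". This is done separately for each arm. SAP 12.1 summarises duration of exposure but does not define it to include time after the last dose.

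**Numerator.** SAP 12.2 limits the AE summaries to treatment-emergent events, which are "those AEs with onset date equal to or after the start date of the study drug". No closing date is given. The events it sets aside are the pre-dose ones: "the AEs occur after signing the informed consent form but before receiving study drug".

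**Collection period.** Protocol 3.3.2.7 records AEs from consent "until the subject is either discontinued from the study or all Week 16 study assessments have been completed" (or until screen failure). The last dose does not end collection.

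**Follow-up after stopping drug.** Protocol 8.1: "If a subject discontinues study drug prematurely for any reason, the subject should be encouraged to remain in the study", with the remaining visits to Week 16 (other than Week 15) to be attended. Protocol 7.6 says the same. Footnote s to the schedule in Protocol 3.2 makes those visits a condition of entering the open-label study. Protocol 7.8 bars from that study anyone who stopped drug for a treatment-related AE, even if all visits are completed.

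**The concern.** A rate per patient-year is meant to make arms with unequal exposure comparable. That works only if the events counted are those that could occur in the person-time counted. Here the design deliberately keeps subjects under AE follow-up after they stop drug. Their later events enter the numerator and their later time does not enter the denominator.

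AEs are the first-listed safety endpoint in both documents, and SAP 12.2 provides for AE rates in each display where suitable. It is the only AE summary described there that adjusts for exposure, so no companion figure would reveal the distortion. If followed time off drug differs between arms, the two rates can differ when the underlying incidence is the same.

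Elsewhere the plan does set such limits. SAP 8.3.1 leaves peak 6MWD assessments made more than 24 hours after the last dose out of the main analyses, and the deaths listing in SAP 12.2 has its own stated period. The AE rate has no equivalent rule.

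**Working it through.** **Inputs from the documents.** Treatment phase of 16 weeks; 1:1 allocation; 314 subjects in total; a discontinuation allowance of about 15% (SAP 5, Protocol 10.2). The plan states no AE rate to reproduce. The 15% does reproduce the sample size: 133/0.85 = 156.5, so 157 per arm and 314 in total. It is not split by arm, nor between stopping drug and leaving the study.

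**Assumptions.** The stop week, the share who stay to Week 16, the split by arm and the AE rates below are illustrations. "On drug" below means on study drug, active or placebo.

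**Formulas.** For a share d stopping at week s, with a share q of them followed to Week 16, the weeks per subject are:
- on drug: T_on = 16(1 − d) + d·s
- followed off drug: T_off = d·q·(16 − s)

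The planned rate is (events on drug + events off drug)/T_on. Relative to the on-drug rate, the inflation factor is 1 + (r_off·T_off)/(r_on·T_on), where r is the AE rate. With r_off = r_on it is 1 + T_off/T_on.

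**One arm, d = 15%, equal AE rates on and off drug.** At s = 8, T_on = 13.6 + 1.2 = 14.8. If all stay, T_off = 1.2 and the factor is 1 + 1.2/14.8 = 1.081. The other cases follow in the same way:

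| Stop week | All stay | Half stay | None stay |
|---|---|---|---|
| 4 | 1.127 | 1.063 | 1.00 |
| 8 | 1.081 | 1.041 | 1.00 |
| 12 | 1.039 | 1.019 | 1.00 |

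**Two arms, no true difference, 20% versus 10% stopping, all stay.** At Week 8:
- 20% arm: T_on = 12.8 + 1.6 = 14.4, T_off = 1.6, factor 1.111
- 10% arm: T_on = 14.4 + 0.8 = 15.2, T_off = 0.8, factor 1.053
- ratio 1.111/1.053 = 1.056

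The ratio is 1.088 for stopping at Week 4 and 1.026 at Week 12. With half retained, the Week 8 ratio is 1.028. With the same stopping, timing and retention in both arms it is 1.00, although both rates are still too high.

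**The same Week 8 case in counts,** with 157 per arm and an assumed 6 AEs per patient-year everywhere:
- 20% arm: 157 × 14.4/52 = 43.5 patient-years on drug and 4.8 off, 289.8 events, planned rate 6.67
- 10% arm: 157 × 15.2/52 = 45.9 on and 2.4 off, 289.8 events, planned rate 6.32
- with all followed time in the denominator: 6.00 in both arms

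**Direction.** Two cases in which the arm with more discontinuation is inflated less:
- 20% stop at Week 8 and leave the study in one arm; 10% stop at Week 8 and stay in the other. The factors are 1.00 and 1.053, ratio 0.95.
- The active on-drug rate is twice placebo, off-drug rates equal placebo's, 15% (active) versus 10% stop at Week 8, and all stay. Active: 1 + 0.5 × 1.2/14.8 = 1.041. Placebo: 1 + 0.8/15.2 = 1.053. An on-drug ratio of 2 would read 2 × 0.989 = 1.98.

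**The case against.** Little formally rests on this rate. Protocol 10.3.4 plans no inferential AE analysis and asks for subject numbers, percentages and event counts; the rate is a SAP addition. Those other summaries do not use the denominator at issue. First-dose, last-dose and last-assessment dates are listed (SAP 9.1), and one planned table gives AEs by dose at onset, so a reader could identify off-drug events. All of this stands and limits the weight of the point, but none of it corrects the rate.

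The sizes also depend on retention. Subjects who leave on stopping drug add essentially nothing, and those who stop for a treatment-related AE have no open-label incentive to stay. This stands too: the full-retention figures are the upper end for a given stop week and equal AE rates on and off drug.

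A reader might infer that the rate is biased against whichever arm has more drug discontinuation, presumably the active arm. The documents do not support that. What drives the error is followed time off drug and the events in it, not discontinuation itself. The plan gives no discontinuation or retention by arm, and the two direction cases in the working go the other way. Measured against the in-study rate, the arm with more followed off-drug time relative to on-drug time is always inflated more, but that need not be the arm with more subjects stopping.

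**Conclusion.** The mismatch follows from the text, and neither document contains a rule that aligns the two periods. The rate exceeds the on-drug rate whenever a followed subject has an AE starting after the last dose.

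The size is modest. At 15% stopping at Week 8 with equal incidence on and off drug, it runs from 0% to 8% according to retention; with full retention and stop weeks from 4 to 12, it runs from about 4% to 13%. Between arms, a ratio of 1.06 arises with no true difference under 20% versus 10% stopping at Week 8 and full retention. These splits are illustrative, because the documents give only an overall 15%.

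The between-arm comparison can therefore be distorted, but neither that it will be nor in which direction can be stated in advance. This is a defect in a descriptive safety measure that should be corrected before unblinding. It does not touch the efficacy conclusions.

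**What to change.** Use one period in both parts of the rate.

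- **Main rate.** Divide all treatment-emergent AEs by patient-years from first dose to the end of AE collection, meaning study discontinuation or completion of the Week 16 assessments. This fits the SAP's own open-ended treatment-emergent definition. With constant incidence the inflation factor becomes 1.00 in each arm, whatever the retention.
- **Optional second rate.** Limit both AEs and person-time to first dose through last dose plus a stated number of days, capped at the end of AE collection. Label it as the on-treatment rate.

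The cost is one SAP sentence and one derived end date. Dosing and last-assessment dates are already listed under SAP 9.1, and Protocol 8.2 records a termination date for subjects lost to follow-up, so no new data collection is needed. The drawback is that the main rate, shown alone, mixes time on and off drug; the second rate answers that if the on-drug rate is of interest.
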